#### INCLUSION CRITERIA:

1. Subject is healthy, as determined by screening evaluation that is not greater than 30 days before the first drug study visit.
2. Subject is male or female between 18 and 65 years of age inclusive.
3. Subject is an acceptable candidate for venipuncture.
4. Subject is willing to stop all non-routine OTC medications, as well as vitamins, dietary supplements, and herbals, for 24 hours prior to study drug administration and during pharmacokinetic study visits.
5. Subject is willing, for each of the four drug study periods, to stop consuming grapefruit, grapefruit products, starfruit, star fruit products, Seville oranges, and St. John's wort from 72-hour before study drug administration until the period's last blood sample.
6. Subject is willing to not smoke (or use e-cigarettes) during study visits.

#### EXCLUSION CRITERIA:

1. Subject has a significant medical disease (including cardiovascular, pulmonary, hematologic, endocrine, immunologic, neurologic, gastrointestinal or psychiatric).
2. Subject shows evidence of congestive heart failure or history of congestive heart failure.
3. Subject exhibits electrocardiogram (12 lead) with clinically significant abnormalities (e.g. QTcF >450 msec).

4. Subject has a history of alcohol or drug abuse, which in the opinion of the investigator, could jeopardize the subject's health or would compromise the subject's ability to participate in this trial.
5. Subject is pregnant, breast feeding, or trying to become pregnant.
6. Female subject of childbearing potential is unwilling or unable to use a medically acceptable method of contraception throughout the entire study period and for one week after the study is completed. Medically acceptable methods of contraception that may be used by the subject and/or her partner are: oral birth control pill, condom with spermicide, diaphragm with spermicide, IUD, vaginal spermicidal suppository, surgical sterilization of patient or their partner(s), abstinence, or hormonal-based patches, ring, injections, and implants.
7. Subject routinely uses (i.e. daily or weekly) prescription medication except hormonal birth control medication, routinely uses (i.e. daily or weekly) OTC medication, or routinely uses (i.e. daily or weekly) St. John's Wort. OTC medications do not include vitamins, dietary supplements, or herbals.
8. Subject routinely uses (i.e. daily or weekly) acid blockers, antacids, anti-diarrhea, stimulants, appetite suppressants, or anti-nausea medication or other drugs that modulate GI function.
9. Subject is currently taking itraconazole or medication known to interact with itraconazole.
10. Subject is allergic to itraconazole.
11. Subject has liver impairment as assessed by alanine aminotransferase (ALT), aspartate aminotransferase (AST), or total bilirubin levels greater than the upper limit of normal (ULN).
12. Subject has renal impairment as assessed by creatinine clearance lower than 50mL/min/1.73m^2, using the CKD-EPI formula.
13. Subject is not willing or able to be adherent to study protocol (e.g. study visits).
14. Subject has a condition in which in the opinion of the PI or medical physician would increase risk to the subject or interfere with the integrity of the study.
15. Subject has received an investigational product within 30 days prior to study drug administration, plans to receive an investigational product during their study participation period, or plans to donate blood to any other clinical trial during their study participation period.
16. Subject has provided plasma donation within 1 month of screening or any blood donation/loss more than 500 mL within 8 weeks prior to study drug administration.

## Monitoring Plan

Data Safety Monitoring will be performed by a physician who is not on the study team. In closed review of subjects (i.e. de-identified data), the physician will review the following information: AEs (recorded on a flow sheet), screen failures, subject withdraws and terminations, and enrollment. Reviewed data will include clinical summaries, enrollment numbers, and adverse events. Additionally, she will conduct such reviews after the completion of the first four subjects, and then quarterly.

## Statistical Analysis Plan

This is a pharmacokinetic, in vitro-in vivo correlation study. The primary outcome will be the assessment of pharmacokinetic area-under-the-curve (AUC) of fast tablet, medium tablet, and slow tablet, with regard to rank-order of point estimates, after a single oral dose of itraconazole in at least n=12 healthy volunteers. It is hypothesized that fast dissolving tablet will provide the highest AUC point estimate value, and the slow dissolving tablet will provide the lowest AUC point estimate value. The point estimate is the simple mean value. There will either be a rank-order correlation or not.

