## PROTOCOL SUMMARY

TITLE OF THE STUDY: Prediction of Itraconazole Oral Absorption From In Vitro Dissolution

PHASE: Phase 4

METHODOLOGY: Randomized, open-label, 4-way, cross-over, four period, fasted single-dose study comparing pharmacokinetic area-under-the-curve (AUC) of fast tablet, medium tablet, and slow tablet.

STUDY CENTER: University of Maryland

NUMBER OF SUBJECTS: at least n=12

STUDY OBJECTIVES: The primary outcome will be the assessment of pharmacokinetic area-under-the-curve (AUC) of fast tablet, medium tablet, and slow tablet, with regard to rank-order of point estimates, after a single oral dose of itraconazole in at least n=12 healthy volunteers. It is hypothesized that fast dissolving tablet will provide the highest AUC point estimate value, and the slow dissolving tablet will provide the lowest AUC point estimate value.

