### Background

Itraconazole is an example drug with low solubility, where the rate of drug dissolution will impact the amount of drug that is absorbed. A measure of the amount of drug that is absorbed is pharmacokinetic area-under-the-curve (AUC). It is hypothesized that fast dissolving tablet will provide the highest AUC point estimate value, and the slow dissolving tablet will provide the lowest AUC point estimate value.

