### Procedures

In this non-treatment, pharmacokinetic study. There will be a screening visit and four pharmacokinetic study arms for all enrolled subjects. Subjects will be enrolled on an ongoing basis until either the anticipated number of required subjects for at least n=12 completed subjects is achieved. In each pharmacokinetic study visit occasion, individual subjects will receive a single dose of one (and only one) of four drug products. The products are fast tablet, medium tablet, slow tablet, and commercial oral solution.

Subjects will be randomized into one of four sequences, A, B, C, or D. Sequence A will receive drug products in the following order: 1, 2, 4, 3. Sequence B will receive drug products in the following order: 2, 3, 1, 4. Sequence C will receive drug products in the following order: 3, 4, 2, 1. Sequence D will receive drug products in the following order: 4, 1, 3, 2. Numbers 1, 2, 3, 4, are Fast tablet, Medium tablet, Slow tablet, and oral solution, respectively.

Each tablet contains itraconazole 100mg, which is sub-clinical in amount. The dose of commercial oral solution (10mg/ml) is also itraconazole 100mg. In each period, blood samples will be collected 0-48 h. Additionally, for oral solution, a blood samples will be collected at 72.0 hr post-dose.

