Standardized meals and snacks will be served during each PK study arm. Meals and snacks include beverages. Four hours after taking test drug, or approximately noon, a lunch will be served. Lunch beverage will only include clear, non-bottled water. Lunch will exclude beverage with low pH (e.g. soft drinks, fruit juices, sport and energy drinks, tea, coffee). An afternoon snack will be served 3 hours later, or at approximately 3pm. Dinner will be served 3 hours later or at approximately 6pm. An evening snack will be served 3 hours later, or at approximately

9pm. While in the GCRC, subjects will fast between meals or snacks except for clear, non-bottled water. However, no water is allowed 1 hour before and after drug administration. There are 4 visits for each tablet arm (i.e. a second, third, and fourth visit of the arm for the 24, 36, and 48 hr blood draws, respectively). There are 5 visits for the oral solution arm (i.e. a second, third, fourth, and fifth visit of the arm for the 24, 36, 48, and 72 hr blood draws, respectively). Subjects will return for the next study arm, preferably 1 week later with a minimum of a wash out of 7 days and no more than 60 days.

Subjects will be monitored for AEs during study days. At each study visit, subjects will be asked about any AE that may have occurred between study visits. At the last study visit, an additional 5 cc (1 teaspoon) will be collected for liver function test safety labs. All AE will be documented in the source documents by research personnel. AEs and SAEs will be reported per UMB HRPO guidelines.

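### Does leaving the AUC limits and a missed 48 h draw unspecified undermine the rank-order result?

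*Combined protocol and SAP*

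**What the plan says.** The Protocol Summary describes the study as "comparing pharmacokinetic area-under-the-curve (AUC) of fast tablet, medium tablet, and slow tablet". The Statistical Analysis Plan repeats this as the primary outcome ("The primary outcome will be the assessment of pharmacokinetic area-under-the-curve (AUC) of fast tablet, medium tablet, and slow tablet") and adds two operating rules: "The point estimate is the simple mean value" and "There will either be a rank-order correlation or not". Neither section writes AUC0-48, AUC to the last sample or AUC to infinity. Nor do they give an integration rule or say how values below the assay limit enter.

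The Procedures section fixes the sampling: "In each period, blood samples will be collected 0-48 h". The post-dose times are 1, 2, 3, 4, 5, 6, 8, 12, 15, 24, 36 and 48 h for every product. A further 72 h sample is taken for the oral solution only. The late tablet draws are separate return visits: "a second, third, and fourth visit of the arm for the 24, 36, and 48 hr blood draws". Enrolment continues until "the anticipated number of required subjects for at least n=12 completed subjects is achieved", and completion is not defined. The Background section calls AUC one measure of the amount of drug absorbed.

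**The concern.** A primary endpoint should be computable in only one way, and here the interval of integration is left unwritten. The verdict is yes or no, decided by the order of three means with no margin, so a small shift in one mean can reverse it when two tablets are close.

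The 48 h sample needs a further visit and could be missed. The plan does not then say whether to take the area to the last sample, leave that one AUC out of its tablet's mean, or leave the subject out of all three means. In an open-label study that choice could be made after the data are seen.

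A lesser worry is interpretation. AUC cut at 48 h depends partly on the rate of absorption, so its order need not match the order of amount absorbed.

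**Working it through.** No figure in the plan bears on this point. The sample size of at least 12 is given without variance, effect size or power, so it cannot be reproduced. Half-life, absorption rate, variability and missed-visit rate below are all assumptions.

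**1. Which AUC the samples support.** The three ranked tablets have identical times, the last at 48 h. The 72 h sample belongs to the solution, which is not ranked. AUC0-48 is therefore the area all three tablets support directly. For comparison, take a one-compartment profile, C(t) = ka/(ka − k) × (e^(−kt) − e^(−ka·t)), with k = ln 2 / half-life. Integrate it by linear trapezoid on the protocol times, with half-life 12 to 40 h and ka of 1.0, 0.5 and 0.2 per h. AUC0-48 is then 94% down to 52% of AUC to infinity. An infinity version would rest on 6 to 48% of area that was never observed, which is a further reason to read AUC as AUC0-48.

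**2. Rate versus extent.** With equal total absorption, the slow/fast ratio of AUC0-48 (ka 0.2 against 1.0) is 0.976 at a 12 h half-life and 0.938 at 40 h. Over a wider grid (half-life 8 to 48 h, slow-tablet mean absorption time 3 to 10 h against 1 h for the fast tablet) it runs from 1.001 to 0.841. The effect is nil to moderate.

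**3. Chance of a missed 48 h tablet draw.** There are 12 × 3 = 36 such draws. If misses are independent with probability p, P(at least one) = 1 − (1 − p)^36:

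| p per draw | P(at least one) |
|---|---|
| 1% | 30% |
| 2% | 52% |
| 5% | 84% |

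If misses cluster within subjects, these figures are too high.

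**4. Shift from one miss.** Under the model in step 1, the 36–48 h segment is 7.3 to 21.2% of AUC0-48. Cutting one subject of average AUC at 36 h moves a 12-subject mean by 0.073/12 = 0.6% to 0.212/12 = 1.8%. If true extents are 1/0.9/0.8, adjacent tablets differ by 10 to 11% (0.9/1 and 0.8/0.9). A shift of this size then matters only when chance has already brought the two means close together.

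**5. Effect on the verdict.** The simulation covered 144 cases of 8,000 runs with n = 12. Half-lives were 8, 24 and 36 h, with three sets of absorption times. Extents were equal or 1/0.9/0.8. Within-subject CV was 20 or 40%, between-subject CV 30 or 60%, and draws were missing at random. With exactly one missed 48 h draw:

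| Handling | Verdict differs from complete data |
|---|---|
| Area to last sample | 0.4–6.3% |
| That AUC left out of its mean | 1.8–13.2% |
| Subject left out of all means | 2.0–12.5% |
| Log-linear fill-in from 24–36 h | 0–0.4% |

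The first three disagree among themselves in 3 to 20% of trials (median 14%). With each draw missed at 2% they disagree in 2 to 13% of trials, and at 5% in 5 to 25%.

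These cases are all ties or near neighbours. With extents 1/0.7/0.4 and the other settings kept (a smaller run of 4,000 per case), disagreement falls to about 0 to 3%.

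**The case for a change.** The best case for a change is that the omission is real, cheap to close and tied to the primary outcome. Nothing in the documents states the interval or the missing-sample rule. The late draws depend on subjects returning, the ranking has no tolerance, and the choice among methods could follow sight of the data. A few lines would settle it without new samples or a new endpoint.

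The factual part of this stands: the text is silent, and a sentence naming AUC0-48 would do no harm. The inference that the result is at risk is weaker.

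- With all 48 h draws present, the missing-sample question has no effect.
- Subjects unwilling or unable to keep study visits are excluded (exclusion criterion 13). The 48 h draw is listed among each tablet arm's visits, so a completed subject plausibly has it. This narrows the gap without closing it.
- The larger mismatches come from throwing data away. The reading closest to an AUC-definition question, area to the last sample, changes the verdict least of the three.
- In tied cases the complete-data verdict is already unstable. That is a property of ranking without a margin, a separate matter that defining AUC would not cure.

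The obvious remedy also gains little that can be demonstrated. A log-linear fill-in looks nearly perfect, but the model that generated the data declines as a single exponential over that stretch and so favours it. Its fallback, leaving the subject out everywhere, is among the most disruptive options at 2.0 to 12.5%. A rule written only for 48 h would not cover a lone missed 24 or 36 h draw, which are also return visits.

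On interpretation, the SAP's hypothesis is worded in terms of AUC point estimates, and the Background presents AUC only as a measure of absorption. The stated conclusion does not depend on equating the two.

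**Conclusion.** This is a gap in detail, not an error. The common 0–48 h schedule leads to AUC0-48, and following the plan on that reading gives a valid ranking of the three tablets. A rare missed return draw is something analysts would handle sensibly and report.

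The conditional risk of a changed verdict after one missed 48 h draw is about 0 to 20%: near zero for widely separated tablets, highest for near-ties, and nil if no draw is missed. That range rests on assumed one-compartment kinetics, assumed extents and CVs, and random missingness. The documents do not say how far apart the tablets are. No change to the plan is called for. The result should simply be read as an order in AUC0-48.

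### The primary yes/no conclusion rests on the order of three simple mean AUCs with no measure of uncertainty, so it cannot tell a real step from noise

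*Combined protocol and SAP*

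**What the plan says.** The Statistical Analysis Plan is one paragraph. It introduces the trial with "This is a pharmacokinetic, in vitro-in vivo correlation study". It then sets the primary outcome as the AUC of the three tablets "with regard to rank-order of point estimates", defines the estimate ("The point estimate is the simple mean value") and closes with a binary verdict: "There will either be a rank-order correlation or not".

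The direction is fixed in advance. The Protocol Summary hypothesizes that the "fast dissolving tablet will provide the highest AUC point estimate value" and that the slow tablet gives the lowest. With three tablets, that is the full order fast > medium > slow.

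The design is described as "Randomized, open-label, 4-way, cross-over, four period, fasted single-dose study", and under Procedures "Subjects will be randomized into one of four sequences, A, B, C, or D". Every subject is therefore meant to receive all three tablets and the oral solution. On sampling, Procedures says: "In each period, blood samples will be collected 0-48 h"; only the solution has a further sample at 72 h. The planned size is at least 12 subjects.

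Neither the Protocol Summary, the Background, the Procedures nor the Statistical Analysis Plan gives an SD, a CV, an interval, a test, a significance level or an analysis model.

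**The concern.** Three means always fall in some order, so the rule returns a verdict however noisy the data are. Followed exactly, the plan tells a reader which order was seen, but not whether either step (fast over medium, medium over slow) is larger than chance variation.

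This cuts both ways. A 'yes' can come from two tablets that do not differ. A 'no' can come from one noisy adjacent pair although the true order is as hypothesized. Because the yes/no is the primary result of a study meant to link dissolution to absorption, readers are likely to give it more weight than it can carry. The within-subject data that would show its precision are collected anyway.

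**Working it through.** The plan states no error rate, power, effect size or variability, so there is no figure of its own to reproduce. The check is the probability that the rule says 'yes'.

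**1. All three tablets equal (no CV needed).** Let D1 = mean fast − mean medium and D2 = mean medium − mean slow. Each subject receives every tablet, so subject effects cancel in the differences. With equal variability, Var(D1) = Var(D2) = 2σ²/n and Cov(D1, D2) = −σ²/n, so the correlation is −1/2. In the normal approximation:

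P(D1 > 0 and D2 > 0) = 1/4 + arcsin(−1/2)/(2π) = 1/4 − 1/12 = 1/6 = 16.7%.

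Symmetry gives the same answer: one of 3! = 6 equally likely orders. The number of subjects does not enter.

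**2. Two adjacent tablets equal, third apart in the hypothesized direction (no CV needed for the limit).** With the gap in units of within-subject SD/√n, the same bivariate normal calculation gives:

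| Gap | 0 | 0.5 | 1 | 2 | 3 | 4 |
|---|---|---|---|---|---|---|
| P('yes') | 0.167 | 0.241 | 0.317 | 0.433 | 0.484 | 0.498 |

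Once the third tablet is clearly separated, the verdict depends only on the equal pair, which is a coin toss: limit 1/2. A fixed true gap grows with √n in these units, so more subjects move the rate toward 1/2.

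**3. Rates in between (assumed CVs).** The documents give none. Assumptions: lognormal AUC, n=12, three subjects in each stated sequence, between-subject CV 60%, within-subject CV 30/40/50%. Simulated 'yes' rates:

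| True simple means, fast:medium:slow | CV 30% | CV 40% | CV 50% |
|---|---|---|---|
| 1:1:1 | 17% | 17% | 17% |
| 1:1:0.9 | 33% | 29% | 27% |
| 1:1:0.8 | 45% | 41% | 37% |
| 1:1:0.5 | 50% | 50% | 50% |
| 1:0.8:0.64 (true order) | 89% | 78% | 68% |

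- Making medium equal to slow instead of fast gives nearly the same rates.
- A between-subject CV of 50% gives 46% at most in the third row. Across 30–90%, the second row spans 26–34% and the third 35–47%.
- The last row means a wrong 'no' in 11/22/32%.
- At 1:1:0.8 and within-subject CV 40%, 'yes' is 41% at n=12, 46% at n=24 and 49% at n=48.

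**4. Where the figures do not apply.** If fast equals slow and medium differs, 'yes' falls below 1/6 (12–15% at 10% apart, 4–10% at 20%). With equal simple means but unequal CVs the 1/6 moves, for example to 10% (fast/medium/slow CVs 30/60/30%) or 22% (60/30/60%).

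**5. How large the noise is.** From a crossover model on ln(AUC) with 30 residual df, the 90% interval for a pairwise ratio is × or ÷ exp[t(0.95, 30) × √ln(1+CV²) × √(2/12)] = 1.23/1.31/1.39. A 20% step is a ratio of 1/0.8 = 1.25, about the same size as this margin.

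**The case against.** The strongest reply is that the outcome is descriptive and the rule answers exactly the question posed: which tablet has the highest and which the lowest point estimate. No significance is claimed, and no treatment or regulatory decision is attached. This stands. It rules out one tempting reading, that the plan breaches a 5% type I error, because the documents set no such level. It does not remove the need for precision beside a descriptive primary result.

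Second, the limit of 1/2 needs two exactly equal tablets and a third far apart. In that case fast over slow is almost always correct and only one adjacent comparison is a coin toss. The tablets were also chosen to differ, and with true 20% steps the rule is right in 68–89% of trials. This stands too. A reader might infer that half of all 'yes' results are false; the documents do not support that, since nothing in them says how likely equality is.

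Third, apart from 1/6 and 1/2, every rate rests on assumed CVs. That is so, which is why ranges are given.

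Fourth, one might require a formal threshold on ln(AUC). That goes too far: the plan names the simple mean, and ln-scale intervals concern geometric means. With equal simple means and CVs of 20/40/60%, the ln model would declare medium above slow in about 16% of trials, against about 7% for paired intervals on simple means.

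**Conclusion.** The concern holds as a weakness in how the primary conclusion is drawn, and it should be fixed. The rule agrees with the hypothesis by chance 1 time in 6 when all tablets are equal, and up to a limit of 1 in 2 when only one adjacent pair is. These two figures rest on similar variability; the second also requires the third tablet to lie in the hypothesized direction. The intermediate rates and the wrong-'no' rates are conditional on the assumed CVs.

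A reader might also infer that 12 subjects are too few. This point does not show that: enlarging the trial leaves the 1/6 unchanged and brings the adjacent-equal case closer to 1/2. What is missing is a statement of precision. The design and data collection are not in question here.

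**What to change.** Amend the Statistical Analysis Plan as follows.

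- Keep the order of the simple means as the descriptive primary result, worded as the 'observed order' in place of a bare yes/no.
- Report each tablet's SD or CV.
- Report 90% intervals for the fast–medium, medium–slow and fast–slow differences in simple means, from the within-subject crossover data. A paired interval is mean difference ± t(0.95, n−1) × SD of the differences/√n. Use AUC over the same 0–48 h interval for all products compared.
- Ratios from a crossover model on ln(AUC) may be added, stated to concern geometric means and not to override the primary estimate.
- In the conclusion, say for each adjacent step whether its interval excludes no difference. Say also that a fast–slow difference alone does not support the three-step order.
- If a label such as 'supported' is used (optional), state its error rate: about 5% per step and about 10% for at least one of the two steps when all tablets are equal with similar variability, and higher with unequal variability.

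The cost is SAP wording and a little more analysis. The downside is a more cautious conclusion. Under the CVs assumed above, at n=12 and true 20% steps, both adjacent intervals would exclude no difference in only about 3–16% of trials with paired simple-mean intervals (4–26% on the ln scale).
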